### Forced Expiratory Volume in 1 second

Measuring FEV1 assesses pulmonary function (airway obstruction, bronchoconstriction or bronchodilation). FEV1 is the volume exhaled during the first second of a forced expiratory manoeuvre, starting from the level of total lung capacity.

### Six-minute Walk Test

The 6MWT measures (Ref: Holland et al 2014) the distance that a patient can quickly walk on a flat, hard surface in a period of 6 minutes. According to the current standard the test should be done twice and the best result is used. It evaluates the global and integrated responses of all systems involved during exercise, including the pulmonary and cardiovascular systems, systemic circulation, peripheral circulation, blood and neuromuscular units and muscle metabolism. The self-paced 6MWT assesses the sub-maximal level of functional capacity and may better reflect the functional exercise level for daily activities.

## **6.2 Safety Variables**

### **6.2.1 Adverse Events**

#### *6.2.1.1 Collection of Adverse Events*

It is the responsibility of the Investigator to collect all AEs (both serious and non-serious) derived by observation, by spontaneous unsolicited reports of patients, and, where appropriate, by routine open questioning, e.g., “How have you felt since I last saw you?”

#### *6.2.1.2 Definitions*

Definitions of AEs and SAEs and their documentation and reporting within this study follow International Conference on Harmonisation (ICH) Good Clinical Practice, European Union, and national regulations and requirements.

An AE is defined as any untoward medical occurrence that occurs in a patient or clinical investigation subject administered a pharmaceutical product, and which does not necessarily have to have a causal relationship with this treatment. An AE can therefore be any unfavourable and unintended sign (including an abnormal laboratory finding), symptom or disease temporally associated with the use of an investigational product, whether or not considered related to the product.

All AEs up to D28 are collected. AEs occurring after D28 should be reported to the Sponsor if the Investigator considers there is a causal relationship with the study drug. All AEs up to D360, which lead to death, are reported as SAEs. Concomitant illnesses, which existed before entry into the study, will not be considered AEs unless there is any deterioration from baseline that is considered clinically relevant or significant during treatment or follow-up period until D28 or discharge from ICU. All AEs must be documented, regardless of the source of identification (e.g., physical examination, laboratory assessment, ECG, reported by patient).

Pre-existing conditions will be recorded in the e-CRF on the Medical History or appropriate page.

Development of barotrauma shall be recorded as an AE.

A TEAE is defined as an AE that begins or that worsens in severity after at least one dose of study drug has been administered up to D28.

See 6.2.1.4 for the schedule of collection of adverse events

### 6.2.1.3 Assessment of Adverse Events

It is recognised that the patient population in the ICU will experience a number of common aberrations in laboratory values, signs and symptoms due to the severity of their underlying disease and the impact of standard therapies. These will not necessarily constitute an AE unless they require significant intervention, lead to discontinuation of blinded study drug or are considered to be of concern in the Investigator's clinical judgement.

Each AE will be assessed by the Investigator with regard to the following categories:

#### 6.2.1.3.1 Seriousness

An SAE is defined as any untoward medical occurrence that at any dose:

- Results in death
- Is life-threatening. This means that the patient is at risk of death at the time of the event. It does not mean that the event hypothetically might have caused death if it were more severe
- Requires inpatient hospitalisation or prolongation of existing hospitalisation
- Results in persistent or significant disability or incapacity
- Is a congenital anomaly or birth defect
- Is an important medical event that may not be immediately life-threatening or result in death or hospitalisation but that may jeopardise the patient or require intervention to prevent one of the above outcomes. Examples of such events are intensive treatment in an emergency room or at home for allergic bronchospasm; blood dyscrasias or convulsions that do not result in hospitalisation; or development of drug dependency or drug abuse

Medical and scientific judgment should be exercised in deciding whether a case is serious and whether expedited reporting is appropriate. However, all deaths up to D360 will be reported as a SAE.

“At any dose” does not imply that the patient is receiving study treatment at the time of the event. Study drug doses may have been given during treatment cycles or interrupted temporarily prior to the onset of the SAE, but may have contributed to the event.

#### 6.2.1.3.2 Intensity

Classical reporting of mild, moderate and severe AEs making reference to the patient's functional status is difficult for a randomised study in critically ill patients. Patients enrolled in this study will primarily be mechanically ventilated and comatose due to their underlying condition and/or the drugs they are prescribed for sedation and analgesia in the ICU. Therefore, the classical approach to AE reporting, which requires patient communication and evaluation of the impact on functioning will be adapted to the ICU environment. The Investigator will be responsible for the assessment of severity, using the categories of mild, moderate or severe to describe each AE as:

- **Mild:** Does not interfere with patient's usual function

- **Moderate:** Interferes to some extent with patient's usual function
- **Severe:** Interferes significantly with patient's usual function

Note the distinction between serious and severe AEs. **Severe** is a measure of intensity whereas an event must meet one of the criteria for serious events listed in Section 6.2.1.3.1 to be considered **serious**; thus, a **severe** reaction is not necessarily a **serious** reaction. For example, a headache may be severe in intensity, but would not be classified as serious unless it met one of the criteria for serious events listed in Section 6.2.1.3.1.

#### 6.2.1.3.3 Causality

The Investigator will assess the causality/relationship between the study drug and the AE and record that assessment in the e-CRF. Causality will be assessed as:

- **Not related:** AE is obviously explained by another cause; OR the time of occurrence of AE is not reasonably related to administration of the study drug
- **Possibly related:** Study drug administration and AE occurrence are reasonably related in time; AND AE is explained equally well by causes other than study drug
- **Probably related:** Study drug administration and the occurrence of the AE are reasonably related in time; AND the AE is more likely explained by exposure to study drug than by other mechanisms

The most likely cause of an AE (e.g., disease under treatment, concomitant disease, concomitant medication, other) will be indicated in the e-CRF with details of the concomitant disease or medication or other cause.

#### 6.2.1.3.4 Clinical Laboratory Adverse Event

Abnormal laboratory findings (e.g., biochemistry, haematology, urinalysis) or other abnormal assessments (e.g., vital signs) that are judged by the Investigator as clinically significant will, if certain requirements are met, be recorded as AEs or SAEs. Clinically significant abnormal laboratory findings or other abnormal assessments that meet the definition of an AE or SAE and are detected during the study, or are present at baseline and significantly worsen following the start of the study, will be reported as AEs or SAEs. However, clinically significant abnormal laboratory findings or other abnormal assessments that are associated with the disease being studied (unless judged by the Investigator as more severe than expected for the patient's condition), or that are present or detected at the start of the study and do not worsen, will not be reported as AEs or SAEs.

The Investigator will exercise their medical and scientific judgment in deciding whether an abnormal laboratory finding or other abnormal assessment is clinically significant.

#### 6.2.1.4 Recording Adverse Events

AE reporting will extend from signing of informed consent. AEs occurring after D28 should be reported to the Sponsor by the Investigator if the Investigator considers there is a causal relationship with the study drug. However, all deaths will be recorded and reported as SAEs throughout the study (up until D360).

All AE reports should contain a brief description of the event, date and time of onset, date and time of resolution, intensity, treatment required, relationship to study drug,

action taken with the study drug, outcome, and whether the event is classified as serious.

Recording a diagnosis (when possible) is preferred to recording a list of associated signs and symptoms. However, if a diagnosis is known but there are associated signs or symptoms not generally attributed to the diagnosis, the diagnosis and each sign or symptom must be recorded separately.

#### 6.2.1.5 Reporting Serious Adverse Events

According to applicable European Union regulations and requirements, an SAE must be reported to the Sponsor from the trial site as soon as possible **within 24 hours** of becoming aware of the SAE. A medically qualified person at the trial site identified on the Delegation of Authority Log with this responsibility must assess the SAE. Any member of the clinical trial site staff can assist in reporting an initial SAE. The Principal Investigator or delegated sub-investigators are responsible for the SAE reporting procedures at the site during the trial, and must always sign-off on each SAE even if other site staff have reported the event on behalf of the investigators. A delegation log at each trial site will clearly show delegation of responsibilities regarding SAE reporting.

The SAE form must be completed with all the relevant information and forwarded to Crown Pharmacovigilance by:

- [REDACTED]
- [REDACTED]

If the SAE is urgently reported by telephone, a paper SAE form must always be completed and forwarded to Crown Pharmacovigilance as soon as possible.

The Investigator and the Sponsor (or Sponsor's designated agent) will review each SAE report and the seriousness and the causal relationship of the event to study treatment will be evaluated. In addition, the Sponsor (or Sponsor's designated agent) will evaluate the expectedness according to the reference document (Investigator Brochure). Based on the Investigator and Sponsor's assessment of the event, a decision will be made concerning the need for further action.

If consensus on the assessment cannot be reached between the parties (e.g., Investigator and Sponsor/Sponsor's delegate), all opinions will be provided in the Council for International Organizations of Medical Sciences Form I report and reporting to the CA and IEC should be based on the highest degree of causality provided.

Details for reporting SUSARs can be found in Section 6.2.1.7.

All SAEs will be recorded that occur between signing of informed consent and D28. Events occurring after D28 and coming to the attention of the Investigator should be reported only if they are considered in the opinion of the Investigator to be causally related to the investigational drug. However, all deaths up to D360 will be reported as SAEs.

All SAEs occurring as described above, must be reported **within 24 hours** by email or fax to Crown Pharmacovigilance.

The minimum information required for an initial report is:

- Details of person sending the report (i.e., name and address of Investigator)

- Patient identification details (screening/randomisation number, age, sex, NOT patient name)
- Protocol number
- Description of SAE
- Causality assessment

However, all points on the SAE form should be covered in the initial report and the completed SAE form itself must be emailed or faxed to Crown Pharmacovigilance. After receipt of the initial report, Crown Pharmacovigilance will review the information and, if necessary, contact the Investigator to obtain further information for assessment of the event. Crown CRO will be responsible for all information processing and reporting according to local legal requirements.

Detailed instructions concerning SAE reporting procedures will be described in a Safety Management Plan written by Crown Pharmacovigilance. SAE Report Form and contact information for reporting SAEs will be provided to the sites.

#### *6.2.1.6 Follow-up of Adverse Events*

All AEs experienced by a patient, irrespective of the suspected causality, will be monitored until: the AE has resolved; any abnormal laboratory values have returned to baseline or stabilised at a level acceptable to the Investigator and Medical Monitor; there is a satisfactory explanation for the changes observed; the patient is lost to follow-up; or the patient has died.

#### *6.2.1.7 Suspected Unexpected Serious Adverse Reactions*

Any AE that is serious, associated with the use of the study drug, and unexpected (SUSAR) has additional reporting requirements, as described below.

- If the SUSAR is fatal or life threatening, associated with use of the study drug and unexpected, regulatory authorities and IECs must be notified **within 7 calendar days** after the Sponsor learns of the event. Additional follow-up information (cause of death, autopsy report and hospital report) should be reported **within an additional 8 days** (15 days total).
- If the SUSAR is not fatal or life threatening but is otherwise serious, associated with the use of the study drug and unexpected, regulatory authorities and IECs must be notified **within 15 calendar days** after the Sponsor learns of the event.

The Sponsor will notify the Investigators in a timely fashion of relevant information about SUSARs that could adversely affect the safety of patients. Follow-up information may be submitted if necessary.

The Sponsor will also provide annual safety updates to the regulatory authorities and IECs responsible for the study. These updates will include information on SUSARs and other relevant safety findings.

#### *6.2.1.8 Pregnancy*

Monitoring of pregnancies is not applicable to this study because pregnancy is an exclusion criterion and a pregnancy test is performed in all women of childbearing potential at screening. Owing to the nature of the study involving short (6-day) treatment with the study drug in an ICU setting, it is not possible for women to become pregnant during treatment and for there to be any foetal exposure to the study drug.

### 6.2.2 Laboratory Variables

The biochemistry and haematology analysis will be performed at the hospital laboratories of the individual Investigator sites. Copies of laboratory accreditation and relevant reference ranges will be provided to the Sponsor or representative prior to the analysis of the first patient sample at that site.

The laboratory variables measured in the study will be as detailed in Table 3.

Blood samples for determination of biochemistry and haematology will be taken at screening, pre-dose on D1 (baseline value) and daily up to D28 while the patient is in the ICU, as detailed in the Schedule of Procedures in Section 7.1, Table 5. The date and time of sample collection will be recorded in the e-CRF.

Dipstick urinalysis will be taken in the ICU (if urine is being produced) pre-dose on D1 (baseline value) and daily up to D28 while the patient is in the ICU, as detailed in the Schedule of Procedures in Section 7.1, Table 5. The date and time of sample collection will be recorded in the e-CRF.

**Table 3 Laboratory Assessments**

6.2.2.1	Haem atolo gy:	Haemoglobin Haematocrit Erythrocytes MCV Platelets Leucocytes Differential counts of: Neutrophils Eosinophils Basophils Lymphocytes Monocytes	6.2.2.2	Bioc hemi stry:	Albumin Creatine kinase Creatinine Glucose Triglycerides Urea Bilirubin Total protein Alkaline phosphatase AST ALT Lactate Sodium (blood gas value acceptable) Potassium Bicarbonate Calcium (total calcium corrected for albumin level) Chloride
6.2.2.3	Urina lysis:	pH Protein Glucose Ketones Bilirubin Blood			
6.2.2.4	Pregn ancy test:	In women with child-bearing potential only. A urine pregnancy test will be performed unless the patient is not producing urine in which case a serum pregnancy test will be performed instead			

*Abbreviations: AST=aspartate transaminase; ALT=alanine transaminase; MCV=mean corpuscular volume.*

A maximum of 100 mL of blood will be taken for study-specific testing during the study in addition to sampling for routine analysis of haematology and biochemistry variables.

### **6.2.3 Vital Signs**

Vital signs will be measured supine pre-dose on D1 (baseline) and daily up to D28 while the patient is in the ICU, as detailed in the Schedule of Procedures (Section 7.1, Table 5). The date and time of collection of each parameter will be recorded in the e-CRF.

Vital sign variables are:

- Blood pressure (systolic, diastolic and mean; mmHg): to be recorded via an arterial line
- Heart rate (HR; bpm): measured as per clinical practice in each ICU
- Total respiratory rate (breaths per minute)
- Temperature (°C): core temperature to be measured according to the site's usual practices and the site of measurement should be recorded in the e-CRF

### **6.2.4 ECG**

Refer to the Schedule of Study Procedures (Table 5) for the timings of individual measurements.

Twelve-lead ECGs will be obtained after the patient has rested in a supine position for at least 10 minutes. All 12-lead ECGs should be recorded while the patient is in the supine position. The investigator or designated physician will review the paper copies of each of the timed 12-lead ECGs on each of the study days when they are collected. ECGs will be recorded at 25 mm/s or at 50 mm/s. If anything clinically significant is observed on the ECG, the investigator will record it as part of the medical history, where the finding represents a change from baseline.

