### **6.3.3 Medical History**

For documentation of the medical history, any relevant previous and ongoing medical conditions with a start date before the time of informed consent should be documented. Conditions that resolved long before informed consent and have no impact on the disease being studied should not be listed.

The medical history should be obtained by inspecting the patient's medical records or by interviewing the patient or their relatives.

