### **5.8.2 Twelve Lead ECGs**

Twelve Lead digital ECG recordings are performed at Day 1 (Pre-dose) then on Day 7.

On each occasion measurements involve recordings of: Ventricular rate, PR, PQ Interval, QRS Duration, QTc and Categorised Normal/Abnormal result. Procedural details are given in the protocol.

The change from baseline (Day 1 Pre-dose) will be calculated.

ECGs are also performed on Days 180 and 360 prior to the Six-minute walk tests to ensure patient safety during that evaluation. The ECG data from these visits will be listed only.

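### Protocol 6.2.4 sends clinically significant ECG changes from baseline to medical history, which contradicts the adverse event and medical history sections and risks under-reporting of Day 7 findings

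*Protocol*

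**What the plan says.** Protocol 6.2.4 deals with any clinically significant observation on a 12-lead ECG and gives it one destination: "the investigator will record it as part of the medical history, where the finding represents a change from baseline". It does not mention adverse events.

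Three other protocol sections govern the same finding:

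- 6.2.1.2, the AE definitions, names ECG as a source: "All AEs must be documented, regardless of the source of identification (e.g., physical examination, laboratory assessment, ECG, reported by patient". It also says what the Medical History page is for: "Pre-existing conditions will be recorded in the e-CRF on the Medical History or appropriate page".
- 6.2.1.3.4 has a laboratory title but covers other assessments too: "Clinically significant abnormal laboratory findings or other abnormal assessments that meet the definition of an AE or SAE and are detected during the study" are to be reported as AEs or SAEs, as are those present at baseline that worsen significantly.
- 6.3.3 sets the scope of medical history: "any relevant previous and ongoing medical conditions with a start date before the time of informed consent should be documented".

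The ECG schedule is short. According to SAP 5.8.2, "Twelve Lead digital ECG recordings are performed at Day 1 (Pre-dose) then on Day 7". Further tracings precede the walk tests on Days 180 and 360, and for those, "The ECG data from these visits will be listed only".

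**The concern.** An ECG abnormality that is absent before dosing and present on Day 7 is the kind of observation a treatment-emergent AE record exists to capture. Section 6.2.4 points it to a form meant for what the patient brought into the trial.

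The choice of form matters because the downstream outputs depend on it. The TEAE and serious TEAE tables (SAP 7.3.1) are built from AE records, and an AE record carries the intensity, causality and seriousness assessments of Protocol 6.2.1.3. A medical history entry carries none of these. SAP 7.2.1.3 reports medical history among the characteristics before treatment start (Tables 14.1.8.1 and 14.1.8.2), so a misfiled Day 7 finding would be shown as a baseline feature.

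Protocol 9.7 requires the protocol to be followed exactly, and 6.2.4 is the section that staff handling an ECG are most likely to consult.

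**Working it through.** No figure is involved; the check is to set the sections side by side.

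1. **What can be a change from baseline?** Protocol 8.2.1.1 defines baseline as the latest valid pre-dose assessment, and SAP 5.8.2 and 5.9.1 take Day 1 pre-dose. Neither Protocol Table 5 nor 7.2.2.1 schedules an ECG at screening. The Day 1 tracing therefore is the baseline and cannot differ from it. The scheduled ECGs that can differ are Days 7, 180 and 360, all after dosing.

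2. **Can such a finding be medical history?** Section 6.3.3 requires a start date before consent. Section 6.3 places medical history among variables assessed only at screening or baseline, and Table 5 schedules it at screening only. A finding that is new on Day 7 fails all three tests. For such a finding, 6.2.4 and 6.3.3 cannot both be followed.

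3. **Is it an adverse event?** If it meets the definition, yes. Section 6.2.1.2 names ECG as a source, and 6.2.1.3.4 covers abnormal assessments other than laboratory tests. An AE that begins or worsens after at least one dose and by Day 28 is also a TEAE. Two filters apply. For common aberrations in ICU patients, 6.2.1.3 says: "These will not necessarily constitute an AE unless they require significant intervention", lead to stopping of study drug, or concern the investigator. Section 6.2.1.3.4 also exempts abnormalities associated with the disease under study unless they are more severe than expected. Some clinically significant Day 7 changes are therefore properly not AEs.

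4. **How much of the ECG schedule is exposed?** Dosing ends on Day 6, so the Day 7 tracing comes 7 − 6 = 1 day after the last scheduled dose. It is the only scheduled post-dose ECG inside the period to Day 28 in which all AEs are collected. Days 180 and 360 fall later, when 6.2.1.4 asks only for deaths and for events judged causally related to study drug. With 300 patients planned, the ceiling is 300 × 1 = 300 Day 7 tracings. There will be fewer in practice, because Section 7 limits assessments up to Day 28 to patients still in the ICU. The documents give no rate of clinically significant ECG change, so the number of findings that might be misfiled cannot be estimated.

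5. **What survives a misfiling?** SAP 7.3.3 summarises ventricular rate and the ECG intervals with change from baseline (Table 14.3.3.1) and the result as Normal, Abnormal NCS or Abnormal CS (Table 14.3.3.2). SAP 7.6 adds a patient listing (16.2.3.3). These show that a tracing was abnormal. As described, they do not give an event, a causality judgement or a seriousness judgement.

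**The case against.** The strongest reply is that the AE duties do not depend on 6.2.4. That section does not say that medical history replaces the AE form. Sections 6.2.1.2 and 6.2.1.3.4 still require a qualifying ECG abnormality to be reported, and the seriousness criteria (6.2.1.3.1) and the 24-hour SAE rule (6.2.1.5) apply regardless. A site that reads the whole protocol would still report the event, and a treatment imbalance in Day 7 ECGs would still show in the ECG tables.

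This limits the consequence, and it stands. A reader might infer that new post-dose ECG abnormalities will be missing from the AE data, or that every clinically significant finding is affected. The documents support neither: the AE sections still bind, and the filters in 6.2.1.3 and 6.2.1.3.4 remove some findings legitimately. Nor can one conclude that the IDMC would lose sight of them. Protocol 3.1 describes its review as AEs and SAEs, 9.8 refers more broadly to safety data, and SAP 6.1.4 leaves the content of its reports to a charter that is not among the documents.

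Two other defences do not stand. Entering the finding on both forms would still breach 6.3.3, and a general AE rule elsewhere does not tell a reader to disregard a specific instruction in the ECG section. One might also suppose that 6.2.4 was meant for the Day 1 ECG compared with the patient's older tracings, but neither document defines baseline in that way.

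**Conclusion.** Section 6.2.4 is wrong as written. On the study's own definition of baseline it applies, among scheduled ECGs, only to post-dose tracings, and it sends their findings to a record reserved for conditions that began before consent. The contradiction with 6.2.1.2, 6.2.1.3.4 and 6.3.3 is certain. The loss of AE data is possible but not certain.

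The realistic harm is that a new Day 7 finding is under-reported in the TEAE tables and goes without causality and seriousness assessment, while the abnormal result itself remains visible in the ECG outputs. This rests on the assumption that some sites act on 6.2.4 without applying the AE sections. Completion instructions or e-CRF checks that are not among the documents could reduce the risk. The point concerns safety recording only and does not touch the efficacy analysis. It should be corrected because the correction is nearly free.

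**What to change.** Reword 6.2.4 so that clinically significant ECG findings that are a change from baseline and meet the AE or SAE definition in 6.2.1.2 to 6.2.1.3.4 are recorded as AEs and assessed for seriousness and causality, and only findings with onset before consent go to medical history. Tying the sentence to the existing definition matters: sending every clinically significant change to the AE page would create a new conflict with the filters in 6.2.1.3 and 6.2.1.3.4.

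Notify sites of the change. SAP 5.4.3.2 already refers to patients who have done the walk test at Day 180 or later, so some are past Day 7 and the rewording alone will not reach their data. Before the Day 90 lock, for example within the blind data review of SAP 6.1.5, check Medical History entries for post-dose onset dates. It would also help to match Day 7 results classed Abnormal CS against the AE listing, and to query any discrepancy with the site.

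The cost is one protocol sentence, one site notice and one data check. Sample size, randomisation and planned analyses are unaffected.
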